5.5. Completion of eDiary Assessments

To ensure patient compliance with the completion of the evening eDiary report, alarms occurring at 7, 8, 9, 10, and 11 PM will be programmed to alert the patient that he/she has not completed the evening eDiary report. Upon completion of the evening eDiary report, the alarm will no longer be active for the remainder of that day. If the patient does not complete the evening report prior to midnight, that day's evening report will no longer be available for reporting by the patient, and all evening assessments for that day will be considered missing.

Patient compliance with the daily eDiary completion requirement will be verified by site staff as specified in the [Schedule of Evaluations](#).

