7.3. Handling of Dropouts/Missing Data Imputation Method

For weekly responder endpoints based on daily eDiary entries (eg, Weekly Abdominal Pain 30% Responder), a patient who reported daily assess for fewer than 4 days during a week within the Treatment Period will be considered a non-responder for that week. A patient will be deemed a weekly non-responder for all weeks following the patient's discontinuation from the study treatment.

Similarly, the weekly symptom score that is calculated using daily eDiary symptom assessments will be the average of available daily assessment records for at least 4/7 records during the relevant week. The weekly symptom score will be set to missing for weeks with fewer than 4 days of daily assessments. For patients who prematurely discontinues the treatment prior to Week 12, the weekly symptom scores will be considered missing for all weeks after the treatment discontinuation.

Unless stated otherwise, missing data will not be imputed.

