7.8.9.2. Analyses of the Key Efficacy Endpoints

Change from Baseline in Abdominal Pain Through the Treatment Period

The overall treatment effect will be evaluated via the comparison between the MD-7246 dose groups and placebo with regard to the weekly change from baseline (CFB) in abdominal pain using a MMRM model, including the weekly CFB score in abdominal pain as dependent variable and treatment, visit week (categorical), and treatment-by-week as fixed effects, patient as a random effect, and the baseline value as a continuous covariate. An unstructured covariance matrix will be used for the MMRM analysis, unless the model does not converge, in which case the compound symmetry will be used.

In this MMRM, a patient in mITT population without any postbaseline abdominal pain score at its worse will be considered missing. For patients with postbaseline abdominal pain scores, at any particular week, if there are fewer than 4 daily scores available, the weekly change from baseline will be considered as missing. Weeks after the treatment discontinuation will be considered as missing.

Descriptive statistics for the overall treatment effect based on the MMRM model will include the least-squares (LS) mean difference between each MD-7246 dose and placebo, LS mean change from baseline for each treatment, their corresponding 95% CIs, and the p-values associated with the comparisons to placebo. In addition, LS Means for the weekly treatment differences between each MD-7246 group and placebo will also be provided with the same set of statistics derived from the same MMRM model defined above and will be plotted based on the MMRM estimates.

Additionally, the non-model based descriptive statistics for the corresponding change from baseline (overall or weekly) will be provided by treatment group in the same tables for the MMRM estimates. Among them, the overall change from baseline is defined as the average of all non-missing post baseline daily scores during the Treatment Period minus the baseline abdominal pain score. The cumulative distribution for the overall change from baseline during the entire treatment period will be summarized and plotted by treatment group.

6/12 Week Abdominal Pain 30% Responder

For the 6/12 Week Abdominal Pain 30% Responder endpoint, the proportion of responders in each MD-7246 treatment group will be summarized and compared to the proportion of responders in the placebo group using a CMH test. The number and percentage of responders,

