A 9/12 Week Abdominal Pain Sustained Responder is a patient who meets the Weekly Abdominal Pain 30% Responder criteria for at least 9 out of the 12 weeks of the Treatment Period.
- 9/12 Week Abdominal Pain 50% Sustained Responder
A 9/12 Week Abdominal Pain Sustained Responder is a patient who meets the Weekly Abdominal Pain 50% Responder criteria for at least 9 out of the 12 weeks of the Treatment Period.
- 6/12 Week Abdominal Discomfort 30% Responder
A 6/12 Week Abdominal Discomfort 30% Responder is a patient who meets the Weekly Abdominal Discomfort 30% Responder criteria for at least 6 out of the 12 weeks of the Treatment Period.
- 6/12 Week Abdominal Bloating 30% Responder
A 6/12 Week Abdominal Bloating 30% Responder is a patient who meets the Weekly Abdominal Bloating 30% Responder criteria for at least 6 out of the 12 weeks of the Treatment Period.
- 6/12 Week Abdominal Cramping 30% Responder
A 6/12 Week Abdominal Cramping 30% Responder is a patient who meets the Weekly Abdominal Cramping 30% Responder criteria for at least 6 out of the 12 weeks of the Treatment Period.
- 6/12 Week Degree of Relief Responder
A 6/12 Week Degree of Relief Responder is a patient who scores ≤ 2 for at least 6 out of the 12 weeks of the Treatment Period.
- 6/12 Week Adequate Relief of IBS Pain Responder

A 6/12 Week Adequate Relief of IBS Pain Responder is a patient who reports adequate relief of IBS pain (“yes”) for at least 6 out of the 12 weeks of the Treatment Period.

The following responder endpoints are defined based on whether a patient satisfies certain criteria for the change from baseline in daily abdominal pain at its worst on at least 50% of protocol defined treatment days (84 days). If a patient did not enter information into the eDiary on at least 42 days during Treatment Period, the patient will not be considered a responder for any of the following responder endpoints. Numbers and percentages of patients satisfying these responder definitions will be summarized by treatment and the comparison between each active treatment group and placebo will be analyzed using a CMH test.

- 50% of Days Daily Abdominal Pain 30% Responder

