A 50% of days Daily Abdominal Pain 30% Responder is defined as a patient who achieves at least 30% decrease from baseline in daily abdominal pain score at its worst for at least 50% of days in the 12-week Treatment Period, which is at least 42 days. These 50% days with at least 30% decrease don’t have to be consecutive during treatment period.

- 50% of Days Daily Abdominal Pain 40% Responder

A 50% of days Daily Abdominal Pain 40% Responder is defined as a patient who achieves at least 40% decrease from baseline in daily abdominal pain score at its worst for at least 50% of days in the 12-week Treatment Period, which is at least 42 days. These 50% days with at least 40% decrease don’t have to be consecutive during the Treatment Period.

- 50% of Days Daily Abdominal Pain 50% Responder

A 50% of days Daily Abdominal Pain 50% Responder is defined as a patient who achieves at least 50% decrease from baseline in daily abdominal pain score at its worst for at least 50% of days in the 12-week Treatment Period, which is at least 42 days. These 50% days with at least 50% decrease don’t have to be consecutive during the Treatment Period.

Additionally, the cumulative distribution of patients satisfying 50% of days daily abdominal pain response based on the percent change from baseline will be plotted and tabulated by treatment group and by percent change from baseline in the daily abdominal pain at its worst.

Abdominal pain is measured daily using an 11-point NRS. Abdominal pain-free days will be those days where the patient reports a score of 0 for abdominal pain at its worst. The post baseline number of abdominal pain-free days per week will be calculated as the number of Abdominal Pain-free Days during the Treatment Period (from the first to the last dose), divided by the total number of days within Treatment Period times 7. The baseline percent number of abdominal pain-free days per week will be calculated as the number of Abdominal Pain-free Days during the Pretreatment Period (per defined Pretreatment Period), divided by the total number of days within the Pretreatment Period times 7. The descriptive statistics (n, mean, SD, median, minimum and maximum) for the baseline and post-baseline abdominal pain-free days

per week and the count of abdominal pain-free days during the Treatment Period will be tabulated by treatment group.

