Assuming the count for the abdominal pain free days follows a Poisson distribution, the post-baseline abdominal pain-free days will be analyzed using a Poisson regression with treatment and baseline number of abdominal-pain free days as the covariates along with an offset variable of treatment duration (in weeks). In the case of overdispersion, the negative binomial model instead of Poisson regression will be implemented. Model estimates for weekly abdominal pain free days will be presented by treatment along with corresponding 95% confidence intervals. In the same table, the difference between the weekly rates for MD-7246 treatment arms and placebo will be represented with corresponding 95% confidence intervals and p-values associated with the comparisons to placebo.

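### The SAP's pain-free-day rate counts every unreported on-treatment day as not pain-free; the protocol divided by days with a pain score, and the change of denominator is not named

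*SAP*

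**What the plan says.** SAP 7.8.9.4 defines pain-free days as "those days where the patient reports a score of 0 for abdominal pain at its worst". The on-treatment weekly rate is that count "divided by the total number of days within Treatment Period times 7", and SAP 7.8.1.1 runs the Treatment Period from first to last dose. The Poisson (or negative binomial) model has "an offset variable of treatment duration (in weeks" and the baseline number of pain-free days as a covariate. The reported result includes "the difference between the weekly rates for MD-7246 treatment arms and placebo". The baseline rate is likewise divided by all Pretreatment Period days.

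Pain scores are collected only in the evening report. Under SAP 5.5, if that report is not completed by midnight, "all evening assessments for that day will be considered missing". The general rule in SAP 7.3 is: "Unless stated otherwise, missing data will not be imputed".

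Protocol 10.4.3 defined a weekly percentage of pain-free days over days with a non-missing pain score. SAP Appendix 1 lists this endpoint under methodologic changes. It covers the new term, the whole-period estimate and the Poisson model, and the reason given is that the events are relatively rare. It does not mention the denominator.

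**The concern.** An unreported on-treatment day adds nothing to the numerator but counts in full in the denominator and the offset. That acts as an imputation of not pain-free, without being described as one. The rate therefore mixes pain relief with diary compliance. The rare-event reason in Appendix 1 does not explain it, because a count model works equally well with reported days as exposure.

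The handling also differs from the key MMRM, where "a patient in mITT population without any postbaseline abdominal pain score at its worse will be considered missing". Here the same patient would enter with zero pain-free days over the full treatment duration.

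At stake is the estimate for one additional endpoint under the pain objective. If completion differs by arm, the comparison can move in either direction without any drug effect. The compliance summaries in SAP 7.8.8 would show such a gap but would not correct the estimate.

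**Working it through.** The documents state no rate, power or completion figure for this endpoint. Completion and pain-free rates below are assumptions.

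**1. Identity.** Let c be the fraction of treatment days with a pain score.

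SAP rate = 7 × pain-free days / all days = c × (7 × pain-free days / reported days).

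One patient, 84 treatment days, 25% of reported days pain-free:

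| Days reported | SAP rate per week | Rate on reported days |
|---|---|---|
| 84 | 7 × 21/84 = 1.75 | 1.75 |
| 76 | 7 × 19/84 = 1.58 | 1.75 |
| 60 | 7 × 15/84 = 1.25 | 1.75 |
| 42 | 7 × 10.5/84 = 0.875 | 1.75 |

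**2. Equal completion.** At c = 0.80, 3.0 versus 2.0 days/week appears as 2.4 versus 1.6. The difference is 0.80 × 1.0 = 0.8, a loss of 20%; at c = 0.90 the loss is 10%. The ratio stays at 1.5.

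**3. Unequal completion, no drug effect, missed days like reported days.** The expected ratio (drug/placebo) is the completion ratio:
- 80% vs 90%: 0.80/0.90 = 0.89
- 85% vs 90%: 0.94
- 87% vs 90%: 0.97
- 85% vs 80%: 1.06, now favouring drug

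**4. Missed days that differ from reported days.** Let k be the chance that a missed day is pain-free, relative to the patient's overall rate. Under no effect, with 80% completion on drug and 90% on placebo:

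all-days ratio = (1 − 0.2k)/(1 − 0.1k)

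non-missing ratio = (0.90/0.80) × that = 1.125 × that

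| k | All days (SAP) | Non-missing days (protocol) |
|---|---|---|
| 0 | 1.000 | 1.125 |
| 0.5 | 0.947 | 1.066 |
| 1 | 0.889 | 1.000 |

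The biases are equal in size on the log scale when the all-days ratio is 1/√1.125 = 0.943, at k of about 0.54. Above that the non-missing version is less biased; below it the SAP version is. For k between 0 and 1 the two bracket the true ratio of 1.

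**5. False positives.** Null simulation with 92 per arm, 84 days, 80% drug versus 90% placebo, two-sided 0.05 and a robust rate-ratio test; 4000 runs per setting. Patient pain-free probabilities were Beta with concentration 1, 3 or 10, which gives the ranges.

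| Pain-free days/week | k = 1, all days | k = 1, non-missing | k = 0, all days | k = 0, non-missing |
|---|---|---|---|---|
| 2 | 11% to 36% | 5% to 6% | 5% to 6% | 8% to 36% |
| 0.5 | 6% to 12% | 5% to 6% | 5% to 6% | 6% to 11% |

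At k = 1 the all-days excess is almost entirely drug looking worse; significant results favouring drug occur 0% to 1.5% of the time. With an 87% versus 90% gap at k = 1, the all-days version gives 5% to 7%.

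These rates come from a robust test, not the SAP's model. A negative binomial fit without the baseline covariate (300 runs, 15% pain-free days, completion varying between patients) gave mean ratios of 0.91 with the SAP offset and 1.02 with reported days, but rejected only 3% and 1% of the time. The bias in the ratio is therefore the firmer result; the error rate depends on the model.

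**6. Baseline.** With the entry minimum of 10 of 14 diary days, the baseline factor is 10/14 = 0.71. This adds noise to the covariate. Baseline reporting precedes randomization, so it does not by itself bias the comparison between arms.

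**The case against.** The strongest reply is that either denominator is a missing-data assumption. The documents say nothing about whether missed days are painful, and if they all are, the SAP version is right and the protocol's is biased toward the less compliant arm. This stands. A reader might infer that the SAP formula generally inflates false claims of benefit; the documents do not support that. In the 80% versus 90% example it works against drug, and false benefit would need poorer reporting on placebo.

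A reader might also infer that the SAP always states when missing counts as failure. It does so for weekly responders. For the 50%-of-days responders it says that with fewer than 42 entries "the patient will not be considered a responder for any of the following responder endpoints", but the fixed 42-of-84-day threshold already ensures this. A patient with 60 reports has 24 missed days counted against response with no further statement. The written denominator for pain-free days can likewise be read as a stated rule. So the contrast with other endpoints carries little weight; the departure from the protocol, unnamed and unjustified, carries the point.

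Nor is it right that no change was declared: Appendix 1 lists the endpoint, and SAP 7.8.9.4 writes out the formula. Only the move from non-missing to all days is missing.

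Finally, treatment is blinded with matching tablets, the diary has hourly evening alarms, and Appendix 1 calls these events relatively rare. A 10-point completion gap is not documented, and 2 pain-free days/week may be high. That limits the likely size but does not remove the mechanism.

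**Conclusion.** The point holds, at modest size. The SAP scores each unreported on-treatment day as not pain-free, departs from the protocol's denominator, and neither names nor justifies that step.

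The attenuation of the weekly-rate difference (10% at 90% completion, 20% at 80%) needs only missed days that resemble reported days. Bias in the ratio also needs unequal completion. The false-positive ranges for all days apply to an assumed 10-point gap with k = 1; they reverse at k = 0, and a 3-point gap is near nominal. They should not be read as the expected error rate of this trial.

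This is one additional endpoint in a study that the SAP itself calls hypothesis generating. The key endpoints, the responder endpoints and the sample size are unaffected.

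**What to change.** For pain-free days only:

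- Restore the protocol's denominator as the main analysis: days with a non-missing pain score, at baseline and on treatment.
- Use log(non-missing days/7) as the offset, and the baseline rate on the same basis as the covariate.
- Treat patients with no post-baseline pain score as missing, as SAP 7.8.9.2 does for the MMRM.
- Keep the all-days version as a supportive table, since for k between 0 and 1 the two bracket the true ratio.
- Name and justify the choice in Appendix 1.
- State that the rule does not carry over to urgent bowel movements and loperamide days. SAP 7.8.10 defines these by reference to pain-free days, but they are entered event by event, so a missed evening report need not erase them.

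The 4-day minimum in SAP 7.3 applies within a 7-day week and should not be borrowed for a 12-week rate (4/84 is about 5%). If a descriptive minimum is wanted, state it as a proportion of treatment days.

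The cost is SAP wording, derivation code and one extra table, with no new data. The main analysis would then assume that unreported days resemble reported ones, and the SAP should say so.

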7.8.10. Exploratory Endpoints and Analyses

The following endpoints will be summarized and analyzed via a similar MMRM for the Change from Baseline in Abdominal Pain through the Treatment Period and at each week:

- Change from Baseline in BM Frequency Rate through the Treatment Period and at each week

For each period of interest (Pretreatment Period, Treatment Period, or a particular week), the BM frequency rate is a weekly rate, which is calculated as the total number of BM within the period divided by the total number of days during the period multiplied by 7. The change from baseline in BM frequency rate is the postbaseline frequency rate minus the baseline frequency rate. For weeks after the treatment discontinuation, this rate will be missing.

- Change from Baseline in BSFS (Stool Consistency) through the Treatment Period and at each week.

For each period of interest (Pretreatment Period, Treatment Period, or a particular week), the BSFS is the average of all available BSFS scores the period. The change from baseline in BSFS is the postbaseline BSFS score minus the baseline score. For weeks after the treatment discontinuation, this score will be missing.

- Change from Baseline in the Percent of Days Experiencing an Episode of Diarrhea through the Treatment Period and at each week

An episode of diarrhea is defined as a sequence of 2 or more loose/watery BMs (BSFS 6 or 7) that are never separated by >1 non-loose/watery stool or by a day without a BM. For each period of interest (Treatment Period, or a particular week), the percent of days experiencing an episode of diarrhea will be calculated as 100 times the number of days with a diarrhea episode divided by the total number of days with study treatment in the period. For baseline, the number of days with a diarrhea episode will be determined for the last 14 days of the Pretreatment Period. The baseline percent of days experiencing an episode of diarrhea will be calculated as 100 times the number of days experiencing an episode during the baseline period divided by the length in days of the baseline period (typically 14 days). The change from

- baseline will be calculated for each week as the weekly percent minus the baseline percent. For weeks after the treatment discontinuation, this percent will be missing.
- Change from Baseline in the Percent of Days Experiencing No Episodes of Diarrhea through the Treatment Period and at each week
- For each period of interest, the Percent of Days experiencing no episode of diarrhea will be 100% minus the percent of days experiencing episode of diarrhea.
- Change from Baseline in BM-related Symptom Severity through the Treatment Period
- Patient global impression of severity (PGI-S) of BM-related symptom severity on a 5-point scale will be reported weekly by eDiary entry. Weekly PGI-S will be summarized weekly and analyzed via MMRM.
- BM-related Symptom Change
- Patient global impression of change (PGI-C) of BM-related symptoms is measured weekly using a 7-point ordinal scale comparing the severity for the past 7 days to the severity before starting the study. The postbaseline weekly PGI-C score will be analyzed via MMRM (without baseline).

Urgent BM Frequency Rate and Number of Days with Use of Loperamide for Diarrhea per week will be defined similarly as Number of Abdominal Pain-free days per week and will be calculated as the total number of events within the entire Treatment Period (or Pretreatment Period for baseline) divided by the total number of days within the Treatment Period, then multiplied by 7. Similar to Number of Abdominal Pain-free Days per week, these endpoints will be summarized by treatment group and the relevant count data during the entire treatment period will be analyzed by Poisson regression for the comparison between any active treatment group and placebo. If the data is skewed to 0 (overdispersed), the Negative binomial model will be used.

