10.4.5 Exploratory Endpoints

Exploratory endpoints related to bowel function will be studied to address the exploratory objective of the study. These non-efficacy endpoints will include:

- **Change from Baseline in BM Frequency Rate at Each Week**
A patient's weekly BM frequency rate is the BM rate (BMs/week) calculated for that week.
- **Change from Baseline in BSFS (Stool Consistency) at Each Week**
Stool consistency is measured using the 7-point BSFS. The patient's BSFS score for each week on treatment is the mean of the non-missing BSFS scores from the BMs reported by the patient during the week.
- **Change from Baseline in Urgent BM Frequency Rate at Each Week**
An urgent BM is a BM that is associated with urgency (ie, the need to rush to the toilet to avoid an accident). A patient's weekly urgent BM frequency rate is the urgent BM rate (urgent BMs/week) calculated for that week.

- **Change from Baseline in the Percent of Days Experiencing an Episode of Diarrhea per Week**
An episode of diarrhea is defined as a sequence of 2 or more loose/watery BMs (BSFS 6 or 7) that are never separated by >1 non-loose/watery stool or by a day without a BM. The Treatment Period percent of days experiencing an episode of diarrhea will be calculated as 100 times the number of days with a diarrhea episode at each week divided by 7. For baseline, the number of days with a diarrhea episode will be determined for the last 14 days of the Pretreatment Period. The baseline percent of days experiencing an episode of diarrhea will be calculated as 100 times the number of days experiencing an episode during the baseline period divided by the length in days of the baseline period (typically 14 days). The change from baseline will be calculated for each week as the weekly percent minus the baseline percent.
- **Change from Baseline in the Percent of Days Experiencing No Episodes of Diarrhea per Week**
Episodes of diarrhea are described above. The percent of days experiencing no episodes of diarrhea per week will be calculated using the same method as described above for episodes of diarrhea.
- **Change from Baseline in BM-related Symptom Severity at Each Week**
BM-related Symptom severity is measured weekly using a 5-point ordinal scale comparing the severity for the past 7 days.
- **BM-related Symptom Change**
BM-related symptom change is measured weekly using a 7-point ordinal scale comparing the severity for the past 7 days to the severity before starting the study.

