5.3.3. Exploratory Assessments

In addition to the key/additional efficacy assessments, the following non-efficacy exploratory assessments are used in determining the exploratory endpoints.

Each day of the Pretreatment and Treatment Periods, the patient will complete eDiary entries on an event-driven basis to report BMs. The patient is also asked to provide assessments of stool consistency and urgency, which are described below. Additionally, the patient will complete eDiary entries on an event-driven basis to report use of loperamide for diarrhea. Patients will complete a daily evening report to enter any BMs and/or loperamide usage not previously reported by the patient for that day (recall is limited to the period of time following the patient’s completion of the previous night’s Evening Report [ie for an Evening Report completed yesterday at 10:00pm, no events can be recorded today with a time preceding 10:00pm yesterday], or time following 7:00pm the previous day in instances where the previous night’s Evening Report was missed by the patient).

Bowel Movement Frequency

The assessment of BM frequency is based on the eDiary questions that record BM date and time. Patients will report BMs on an event-driven basis. An evening report will ask whether the patient entered all BMs for that day, and collect BMs not previously entered.

Stool Consistency (5-point ordinal scale)

Patient assessment of stool consistency will be collected using two eDiary questions recorded on an event-driven basis (ie, for each BM reported in the eDiary). For each BM, patients will assess stool consistency by daily eDiary entry using a 5-point ordinal scale:

“How would you describe the consistency of your stool?”

1=Very hard

2=Hard

3=Neither too hard nor too soft

4=Loose but not watery

5=Very loose and watery

The patient also assesses his/her stool consistency using the 7-point Bristol Stool Form Scale (BSFS) described below.

Stool Consistency (BSFS)

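### BM rate and diarrhea-day percent use denominators that ignore diary completion, so an on-treatment week with no diary entries scores as 0 BMs and 100% diarrhea-free days

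*SAP*

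**What the plan says.** **Denominators.** SAP 7.8.10 defines the BM rate as "the total number of BM within the period divided by the total number of days during the period", multiplied by 7. The diarrhea-day count is "divided by the total number of days with study treatment in the period". Diarrhea-free days are the complement: "the Percent of Days experiencing no episode of diarrhea will be 100% minus the percent of days experiencing episode of diarrhea". Protocol 10.4.5 used a fixed week: "the number of days with a diarrhea episode at each week divided by 7". Urgent-BM and loperamide-day rates (end of SAP 7.8.10) are event totals over all days of the Treatment Period.

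**Missing-data rules.** For BM rate, 7.8.10 gives only "For weeks after the treatment discontinuation, this rate will be missing". For diarrhea days it gives only "For weeks after the treatment discontinuation, this percent will be missing". SAP 7.3 has a diary minimum, but for symptom scores averaged from daily ratings: "The weekly symptom score will be set to missing for weeks with fewer than 4 days of daily assessments". SAP 7.8.9.2 repeats it for daily abdominal pain scores.

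**Data capture.** Under SAP 5.3.3, patients enter BMs as they happen, and the evening report picks up any not yet entered. After a missed report, late entry reaches back only to 7 pm of the day before ("or time following 7:00pm the previous day in instances where the previous" night's report was missed).

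**The concern.** A day with no BM entry and no evening report is a day about which nothing is known. The formulas count it in the denominator with zero BMs and no diarrhea. Because the resulting week is a number and not a missing value, the MMRM takes it as observed.

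The direction matters. In the responder endpoints, sparse diary data count against the patient. Here they read as fewer BMs and less diarrhea, which in this population is improvement. Whether MD-7246 changes bowel function is the stated exploratory objective (SAP 2), and the formulation is meant to have little secretory effect. More diary gaps on active drug could hide a secretory effect; more gaps on placebo could create the appearance of one.

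**Working it through.** The documents state no figure for this point, so there is nothing of the plan's own to reproduce. The formulas come from SAP 7.8.10. The BM rates, diarrhea-day percents and gap frequencies below are assumptions, because neither document gives any.

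**1. Full on-treatment week, no diary entries.**
- BM rate = (0 / 7) × 7 = 0 BMs/week.
- Diarrhea days = 100 × 0 / 7 = 0%.
- Diarrhea-free days = 100 − 0 = 100%.

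With no real change and a fully recorded baseline of 14, 21 or 28 BMs/week (2, 3 or 4 per day), this week enters as a change of −14, −21 or −28. With true diarrhea days of 30%, 50% or 70%, it enters as −30, −50 or −70 points.

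**2. Week with three days lacking both entries and a report.** If BMs are evenly spread, the recorded share is 4 / 7 = 0.571, an understatement of 42.9%. At 3 BMs/day the rate is (12 / 7) × 7 = 12, where the true rate is 21. At 50% true diarrhea days, and ignoring any effect on episode linkage, the result is 50 × 4 / 7 = 28.6%.

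**3. Baseline.** Protocol 6.1 (criterion 10) requires evening reports on at least 10 of 14 days. If the other four days also have no entries, the baseline rate is 10 / 14 = 71% of the truth: 15 where the true rate is 21. Against that baseline, a 4-of-7-day week gives 12 − 15 = −3 and an empty week gives 0 − 15 = −15, with no real change. Treatment weeks have no minimum, so baseline gaps do not reliably cancel on-treatment gaps.

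**4. Arm means and the contrast.** If a share m of on-treatment weeks is empty, the simple mean over weeks shifts by −m × true rate.

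| Assumed true BMs/week | m = 5% | m = 10% | False difference, 5% vs 10% |
|---|---|---|---|
| 14 | −0.70 | −1.40 | 0.70 |
| 21 | −1.05 | −2.10 | 1.05 |
| 28 | −1.40 | −2.80 | 1.40 |

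For diarrhea days at an assumed 50%, the same 5-point difference in empty weeks gives 0.05 × 50 = 2.5 percentage points. If m is the same in both arms, the shifts largely cancel.

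**5. Episode linkage.** Under 7.8.10 a BM-free day ends a diarrhea episode. Suppose one loose BM is recorded on Monday and one on Wednesday, with nothing known about Tuesday. Read as BM-free, Tuesday breaks the sequence, and Monday and Wednesday can lose diarrhea status too.

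**6. What is not affected in this way.** Weekly Bristol (BSFS) scores are means of recorded BMs, so an empty week is missing there. The abdominal pain endpoints have the 4-day rule.

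**The case against.** The SAP nowhere says in words that an empty week is scored as zero. It says in 7.3 that missing data are not imputed by default, and it analyzes these endpoints with an MMRM similar to the one for pain, whose section sets weeks with fewer than 4 daily scores to missing. One could argue that the rule carries over. But it is written for daily scores, BMs are event counts, and 7.8.10 restates only the discontinuation rule. Even if it did carry over, the denominator would stay wrong in weeks with 4 to 6 reported days.

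Other objections stand and limit the point:
- BMs entered when they occur remain in the data without an evening report. A reader might infer that three missed reports cost 43% of the week's BMs; that needs three days with no event entries as well.
- A reader might infer that both endpoints divide by all calendar days. The diarrhea denominator is days with study treatment. It is still blind to diary gaps.
- A reader might infer that a bias of 1 or 2 BMs/week is to be expected. The documents support no such figure, and within-arm shifts reach the contrast only to the extent that gaps differ by arm.
- There are controls: the 10-of-14-day entry rule, evening alarms, site checks of compliance, and weekly compliance summaries (SAP 7.8.8). They may reduce gaps or reveal them; they do not correct the endpoint.
- The endpoints are exploratory, and the protocol's diarrhea-day formula also divided by 7 without a minimum. That limits the priority of the point but does not make the formula right.

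**Conclusion.** The point holds. Applied literally, SAP 7.8.10 turns an on-treatment week with no diary entries into 0 BMs/week, 0% diarrhea days and 100% diarrhea-free days. It understates the BM rate by about 43% when three days of a week have neither entries nor a report and BMs are evenly spread. Those results follow from the stated formulas.

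The effect on treatment comparisons is conditional. It requires diary gaps that differ by arm, and its size is illustrative: about 0.7 to 1.4 BMs/week for a 5-point difference in empty weeks at an assumed 14 to 28 BMs/week. The documents do not show that gaps will be common or unequal. The key pain endpoints are not touched. The change is still worth making, because the error runs in the direction of benefit on the bowel-function objective and is cheap to remove.

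**What to change.** Amend SAP 7.8.10 before unblinding:
1. **Rates and percents.** Use days with a completed evening report, already defined in SAP 7.8.8, as the denominator. For the rate, count BMs on those days only.
2. **Minimum.** Require at least 4 such days in a week; otherwise set the week to missing. SAP 7.8.8 already tabulates how many patients reach 4 reports each week.
3. **Baseline.** Use the same diary-day denominator over the 14 days.
4. **Diarrhea episodes.** Keep every recorded BM when deciding whether a sequence continues; dropping entries made on days without a report could split true episodes. Treat a day with no report and no entries as unknown, so that it does not count as BM-free.
5. **Urgent-BM and loperamide-day rates.** Use the same diary-day denominator, or the corresponding offset in the count model.

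The cost is SAP wording and programming; no new data are needed. The downside is that some event entries are not used in the rate and some sparse weeks become missing. The rate for a partly reported week then assumes that unreported days resemble reported ones.
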